Title of the study: The Pull Test To Determine Responders To Subacromial Injection In Patients With Shoulder Impingement

Trial registration: NCT02686671

Date: September 10, 2019

The study took place at Advanced Physical Therapy of Alaska facilities in Anchorage, Alaska.

Between March 2016 and October 2016, two investigators performed the following clinical tests to determine inter-examiner reliability using nine patients with lateral shoulder pain from a local physical therapy outpatient clinic: (1) shoulder flexion, external rotation, abduction and internal rotation passive ROM; (2) Spurling test; (3) Hawkins-Kennedy test; (4) Neer impingement test; (5) painful arc of abduction; and (6) Pull Test, which has been proposed as an shoulder impingement clinical test to differentiate SA bursitis from rotator cuff conditions. Following reliability testing, 29 participants were included from a consecutive convenience sample of 38 patients scheduled for fanwise SA CSI between the periods of January 2017 and February 2018. Past medical history was screened for inclusion and exclusion criteria.

For inclusion, the following criteria were: (1) age 18 to 80 years; (2) one or more positive shoulder clinical tests out of the following: Hawkins-Kennedy test, Neer impingement test, and painful arc of abduction; (3) lateral shoulder pain between 2/10 and 10/10 on Numeric Pain Rating Scale (NPRS) during resisted shoulder abduction; and (4) SPADI (total) score greater than or equal to 20.

For exclusion, the following criteria were: (1) large three-dimensional limitation with any passive range of motion (ROM) of the shoulder as compared to the contralateral side, to rule out adhesive capsulitis; (2) shoulder surgery within the last six months; (3) CSI to the involved shoulder within the past three months; (4) systemic inflammatory condition; (5) radiculopathy during cervical spine active ROM; (6) cervical spine pain as a primary complaint (7) lateral shoulder pain reproduction during Spurling test; (8) inability to undergo a follow-up phone call; (9) neurological disorders that would prevent clinical test performance and (10) pregnancy by self-report.

Study Design

A non-randomized, exploratory study, with repeated measures for pain and disability, was conducted to identify variables associated with successful fanwise subacromial (SA) corticosteroid injection (CSI) in participants with lateral shoulder pain.

Testing Sequence

Each participant read slide presentation print-outs explaining study procedures followed by informed consent and medical history questionnaire. A pre-CSI pain questionnaire for average and current shoulder pain (Numeric Pain Rating Scale, NPRS) and Shoulder Pain and Disability Index (SPADI) were then completed to identify changes over the follow-up period.

Prior to their scheduled fanwise SA CSI as part of their plan of care, each participant within a private treatment room underwent a series of cervical and shoulder clinical tests similar to those performed during the reliability portion of testing by Investigator 1. For

the first two tests, participants exhibiting three-dimensional limitations of passive range of motion (ROM) within any plane indicative of adhesive capsulitis and/or a positive Spurling test were excluded from the study. If passive ROM and Spurling test were negative, the following shoulder clinical tests were performed with at least one required to be positive to participate further: (1) Hawkins-Kennedy test; (2) Neer impingement test; and (3) painful arc of abduction. Next, the Pull Test, involving comparison of shoulder pain produced between resisted shoulder abduction alone at 0° shoulder abduction and resisted shoulder abduction simultaneous with manually-performed humeral long-axis traction by the investigator was performed. Force level for resisted shoulder abduction alone was measured using a dynamometer (Chatillon® DF II Series Digital Force Gauge). For resisted shoulder abduction with traction, traction force was applied at mid-humerus level by one of the investigator's hands. The traction amount was determined by the maximum sulcus distance obtained between the lateral acromion and humerus monitored by the investigators' thumb of the other hand, with no inferior movement of the shoulder girdle detected. The participant was instructed to push outward from their distal humerus into the chest of the investigator positioned adjacent for this portion of the Pull Test. Maximum resisted shoulder abduction, with force level recorded, was the final test performed.

Following clinical testing, each participant underwent fanwise SA CSI using a blind lateral approach performed by a pain medicine physician or physician assistant with over 30 years of experience. For the CSI, a standard solution consisting of 9cc of 0.25% bupivacaine with 1:200,000 epinephrine and 40 mg of triamcinolone (Kenalog®) was administered using a 9 cm 22- or 25-gauge needle. Manually-performed humeral long-axis traction was performed by a medical assistant when a patient was unable to relax, which can affect the entry point into the AHI.

Approximately 30-minutes post-CSI (to allow for anaesthetic to take effect and post-injection vital signs to be charted by a medical assistant), Investigator 2 performed the previous series of shoulder clinical tests in the same order except for shoulder passive ROM and Spurling test, which were not performed. The Pull Test was not performed, however, resisted shoulder abduction alone was included as a test to compare with the pre-CSI result. The second investigator was blind to the results of pre-CSI testing with exception of force applied during resisted shoulder abduction pre- CSI, with a similar force used for resisted shoulder abduction post-CSI to identify pain level change. Maximum resisted shoulder abduction was performed last with force and pain level recorded. One-week and six-week phone follow-ups were conducted post- CSI. Each participant was allowed to continue their current physical therapy regimen if applicable.

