Title of the study: The Pull Test To Determine Responders To Subacromial Injection In Patients With Shoulder Impingement

Trial registration: NCT02686671

Date: September 10, 2019

The study took place at Advanced Physical Therapy of Alaska facilities in Anchorage, Alaska.

Statistical Analysis

Data were analyzed using SPSS software (version 20.0). Descriptive statistics were used to record demographic characteristics, Numeric Pain Rating Scale (NPRS) and Shoulder Pain and Disability Index (SPADI) scores.

Inter-examiner **reliability** was assessed using kappa and percent agreement. **Friedman test, with Wilcoxon signed-ranks test** for pairwise comparisons, was used to determine if SPADI (total) score and average NPRS demonstrated significant changes over time. Effect size (r) was calculated to determine the magnitude of the difference for each pairwise comparison. Mean differences (Mann-Whitney) in average NPRS and SPADI (total) score for positive and negative Pull Test groups were analyzed for follow-up periods. Effect size estimates of variance (r^2) were calculated to identify the percentages of variability in the dependent variables (SPADI, NPRS) explained by each Pull Test group.

Fisher's exact test was calculated to evaluate dichotomous variable association, including clinical test outcomes, gender, and hand dominance, with SPADI (total) score one-week and six-week post-CSI. **Univariate regression** was used to determine if demographics, clinical variables and clinical tests were predictive of successful response one-week and six-week post-CSI ($p \leq .200$). Sensitivity, specificity, positive and negative predictive values, positive and negative likelihood ratios, and odds ratios were calculated for shoulder clinical tests.

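### Does the undescribed push force in the traction half of the Pull Test undermine the planned Pull Test analyses?

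*Protocol*

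**What the plan says.** The protocol's Testing Sequence section describes the Pull Test as two contractions compared on pain: resisted abduction alone, and resisted abduction while the investigator applies long-axis traction to the humerus. For the first, "Force level for resisted shoulder abduction alone was measured using a dynamometer". For the second, the participant is told to "push outward from their distal humerus into the chest of the investigator positioned adjacent for this portion of the Pull Test". One of the investigator's hands applies the traction. The gap under the acromion is monitored with the "thumb of the other hand, with no inferior movement of the shoulder girdle detected". That rule governs how much traction is given; it does not govern how hard the participant pushes.

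Three further contractions are described. Before the injection, "Maximum resisted shoulder abduction, with force level recorded, was the final test performed". About 30 minutes after it, a second investigator repeats resisted abduction alone, "with a similar force used for resisted shoulder abduction post-CSI to identify pain level change". Finally, "Maximum resisted shoulder abduction was performed last with force and pain level recorded". The Pull Test itself is not repeated after the injection.

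The SAP uses the Pull Test result as a grouping variable: differences in "average NPRS and SPADI (total) score for positive and negative Pull Test groups were analyzed for follow-up periods". It also plans variance-explained estimates for the Pull Test groups, Fisher's exact tests, univariate regression, and sensitivity, specificity, predictive values, likelihood ratios and odds ratios for the shoulder clinical tests.

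**The concern.** A comparison of two contractions isolates what differs between them only if the rest is alike. Here one push is gauged and the other goes into an investigator's chest with no force stated. A participant who pushes less hard under traction may report less pain for that reason alone; one who pushes harder may report more. Either could move the person between the positive and negative groups that the SAP compares.

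The protocol also appears to accept the principle. For its before-and-after pain comparison it tells the second investigator the earlier force, the only pre-injection result not withheld, so that a similar force can be used. It seems odd not to take the same care inside the test named in the study title. If the report went on to say that traction relieves pain in those who respond to injection, the design could not support that reading.

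**Working it through.** **1. Count the contractions and their force provisions** (protocol, Testing Sequence and the account of post-injection testing).

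| Contraction | Force provision described |
|---|---|
| Abduction alone, before injection | Measured by dynamometer |
| Abduction with traction, before injection | None |
| Maximum abduction, before injection | Recorded |
| Abduction alone, after injection | Similar to the earlier force |
| Maximum abduction, after injection | Recorded |

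Four of five have a provision. The reliability phase lists the Pull Test without procedural detail, so it neither adds to the count nor fills the gap.

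**2. Ask what the four provisions do.** None states a force level. Two record a maximal effort and one measures a push with no target. Only one matches a force, and it does so for a contrast between two investigators about 30 minutes apart. The protocol describes a use for the dynamometer reading from abduction alone: it lets the second investigator reproduce that push. The traction contraction is never repeated after injection, so it needs no such reference. Its two halves come from one investigator in one session.

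**3. Ask whether any planned analysis needs the change in pain to be due to traction.**

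- The stated aim is exploratory: to find which variables go with a successful injection.
- The Mann-Whitney comparisons, r², Fisher's tests and regressions relate the observed Pull Test result to later outcomes.
- Sensitivity, specificity, predictive values and likelihood ratios describe the observed test.

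All of these concern the test as performed, including whatever push it produced. The result is also fixed before the injection, so later response cannot influence the grouping.

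**4. Try to size the effect.** Suppose, as an assumption, that pain changes by a share b of the proportional change in push. At baseline pain P, the push difference d that moves the reading by one point is d = 1/(b × P). The entry criterion is "lateral shoulder pain between 2/10 and 10/10 on Numeric Pain Rating Scale (NPRS) during resisted shoulder abduction", so take P = 2, 6 (the midpoint) and 10.

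- b = 1: 1/2 = 50%, 1/6 = 17%, 1/10 = 10%.
- b = 0.5: 1/1 = 100%, 1/3 = 33%, 1/5 = 20%.
- b = 0: no push difference has any effect.

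The documents give no value for b, no traction-condition forces, and no pain-change cut-off that would make one point matter. At 10/10 the reading can only fall. One regrouped participant is 1/29 = 3.4% of the sample, but nothing shows that anyone would be regrouped. The calculation therefore gives neither a bias nor a misclassification rate.

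**5. Ask what matching the force would buy.** With equal push, the halves would still differ in the hand contact at mid-humerus and the palpating thumb. The traction would still be set by palpation rather than by measured force. No random order of the halves and no blinding between them is described. Equal push alone would not isolate traction.

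**The case for a change.** The strongest case for acting is that the study's own practice treats force matching as necessary for reading a change in pain, and the Pull Test is a reading of a change in pain. The protocol also mentions that the test has been proposed to separate bursitis from rotator cuff disorders, so what a positive result means is of interest. Nor does the planned kappa fully answer the point. Variation in push that changed the classification between examiners would tend to lower agreement, but a shift common to both would pass unseen, and the reliability sample is only nine patients.

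Much of this stands. The protocol's silence is a real gap in standardisation, and a pain difference should not be credited to traction as such. Two things do not follow. Silence does not show that the forces differed. And the bursitis-versus-cuff remark is background: neither document plans an analysis that tests it or depends on a mechanism.

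The redesign also has a price. With both the investigator's hands occupied, resistance from the chest is part of the test as described. A gauge between arm and chest would need a feasibility check, possibly a holder or a second person, and would give a longer test less like bedside use. Keeping the simple form is a fair trade-off for a study of whether a clinical test predicts response.

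**Conclusion.** The description is incomplete, but no planned result is shown to be wrong and no change to the plan is called for. One contraction of five lacks a force provision. The size and direction of any effect on the Pull Test groups cannot be determined from the documents. The estimates of association and accuracy remain interpretable for the test as performed, and matching force would alter that test without isolating traction. Participants were drawn from injections scheduled between January 2017 and February 2018, so a new set-up could not alter these data.

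This conclusion assumes that the results are reported as the predictive performance of the test and not as evidence of a traction mechanism. Under that reading, analysts lose nothing by stating whether a push force under traction was recorded and, if it was not, noting the limitation in a sentence. That is ordinary reporting and alters no analysis. Matched force in future use would be an optional refinement, subject to feasibility.

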Title of the study: The Pull Test To Determine Responders To Subacromial Injection In Patients With Shoulder Impingement

Trial registration: NCT02686671

Date: September 10, 2019

The study took place at Advanced Physical Therapy of Alaska facilities in Anchorage, Alaska.

Statistical Analysis

Data were analyzed using SPSS software (version 20.0). Descriptive statistics were used to record demographic characteristics, Numeric Pain Rating Scale (NPRS) and Shoulder Pain and Disability Index (SPADI) scores.

Inter-examiner **reliability** was assessed using kappa and percent agreement. **Friedman test, with Wilcoxon signed-ranks test** for pairwise comparisons, was used to determine if SPADI (total) score and average NPRS demonstrated significant changes over time. Effect size (r) was calculated to determine the magnitude of the difference for each pairwise comparison. Mean differences (Mann-Whitney) in average NPRS and SPADI (total) score for positive and negative Pull Test groups were analyzed for follow-up periods. Effect size estimates of variance (r^2) were calculated to identify the percentages of variability in the dependent variables (SPADI, NPRS) explained by each Pull Test group.

Fisher's exact test was calculated to evaluate dichotomous variable association, including clinical test outcomes, gender, and hand dominance, with SPADI (total) score one-week and six-week post-CSI. **Univariate regression** was used to determine if demographics, clinical variables and clinical tests were predictive of successful response one-week and six-week post-CSI ($p \leq .200$). Sensitivity, specificity, positive and negative predictive values, positive and negative likelihood ratios, and odds ratios were calculated for shoulder clinical tests.

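### The SAP measures the size of paired change by a unit-free effect size r that levels off among large gains, and it names no paired change in points with a confidence interval

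*SAP*

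**What the plan says.** The SAP's Statistical Analysis section applies a Friedman test to SPADI total and average NPRS, with Wilcoxon signed-ranks tests "for pairwise comparisons, was used to determine if SPADI (total) score and average NPRS demonstrated significant changes over time". It then assigns one quantity to the size of those changes: "Effect size (r) was calculated to determine the magnitude of the difference for each pairwise comparison". No formula, denominator or interpretive threshold for r is given.

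The only other summary relevant to within-patient change is general: "Descriptive statistics were used to record demographic characteristics, Numeric Pain Rating Scale (NPRS) and Shoulder Pain and Disability Index (SPADI) scores". No change score, confidence interval or location estimate is named.

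The Protocol supplies the setting. Scores are taken before injection, and "One-week and six-week phone follow-ups were conducted post- CSI", so each outcome has three pairwise comparisons. The sample is given as "29 participants were included from a consecutive convenience sample of 38 patients", so there are at most 29 pairs. Entry required a "SPADI (total) score greater than or equal to 20".

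**The concern.** The stated purpose of r is to convey how large each change was. Beside a Wilcoxon test, r normally means Z/√N, and Z uses only the signs of the changes and the ranks of their absolute sizes. It carries no information in SPADI or NPRS points. Once every change has the same sign, the statistic is at its maximum, and a further shift of all patients cannot raise it.

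At stake is how the pre-to-post results are read. A high r could be taken as a statement about how much patients improved, when in the upper range it no longer responds to that. Because the denominator is unstated, the same data can also give two values of r.

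**Working it through.** The documents state no value of r and no SD of change, so there is no plan figure to reproduce. The check works out what r can do with the planned sample.

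**Inputs from the documents.** n = 29 participants (Protocol, opening section); Wilcoxon signed-ranks test and r (SAP, Statistical Analysis); three visits (Protocol, Testing Sequence).

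**Assumptions.** r = Z/√N; changes normally distributed with SD 5, 10, 15 or 20 points; complete follow-up.

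**Step 1: the ceiling without ties.**
- Null mean of the signed-rank sum: n(n+1)/4 = 29 × 30/4 = 217.5.
- Null SD: √[n(n+1)(2n+1)/24] = √(29 × 30 × 59/24) = √2138.75 = 46.25.
- If all 29 improve, the sum is 29 × 30/2 = 435, so Z = (435 − 217.5)/46.25 = 4.70.
- r = 4.70/√29 = 0.873 with N as pairs, or 4.70/√58 = 0.618 with N as observations. The two conventions differ by √2 = 1.41.
- Losses to follow-up barely move the ceiling: 0.877 / 0.620 with 20 pairs and 0.874 / 0.618 with 25.

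**Step 2: shifting the changes when all are positive.** Taking 29 untied changes spread evenly within ±2.5 points of their mean, and moving that mean to 3, 10, 20 and 47 points, gives r = 0.873 / 0.618 every time.

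Ties alter the ceiling without reflecting the size of the gain. If all 29 changes are identical, r = 1.000 / 0.707 whether each is 3 or 47. In one whole-number example in which everyone improved, a mean gain of 3.0 gave r = 0.893 and a mean gain of 47.4 gave 0.874.

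**Step 3: ordinary variability.** Mean r (N = pairs) over 2,000 simulated samples of 29 in each setting:

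| Assumed SD | Gain 3 | Gain 10 | Gain 20 | Gain 30 | Gain 47 |
|---|---|---|---|---|---|
| 5 | 0.52 | 0.87 | 0.87 | 0.87 | 0.87 |
| 10 | 0.28 | 0.73 | 0.87 | 0.87 | 0.87 |
| 15 | 0.19 | 0.56 | 0.82 | 0.87 | 0.87 |
| 20 | 0.14 | 0.45 | 0.72 | 0.84 | 0.87 |

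At SD 15 all 29 patients improved in 51% of samples with a 30-point mean gain and in 98% with a 47-point gain. The ceiling is nearly reached from about 20 points at SD 10 and about 30 points at SD 15. Below that, r rises clearly with the gain.

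**Step 4: what the descriptive scores add.** Visit means give the mean change by subtraction if the same patients are seen at both visits. They do not give its uncertainty: the variance of a paired change is s₁² + s₂² − 2ρs₁s₂, and separate visit summaries do not supply the within-patient correlation ρ.

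**The case against.** The strongest reply is that the flat behaviour needs nearly everyone to improve, and that a small mean gain does not produce this at ordinary spreads. That stands. A reader might infer from Step 2 that r cannot tell a 3-point gain from a 47-point gain. The documents do not support this as a general statement: at assumed SDs of 5 to 20, a 3-point gain gives a mean r of 0.14 to 0.52, well below 0.87. The equality at 3 and 47 points holds only when every patient improves and the tie patterns match, which at a 3-point mean needs changes that vary very little. Nor does it follow that r is uninformative whenever most patients improve.

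A reader might also infer that the trial cannot say how much SPADI or NPRS changed. The SAP's descriptive statistics cover both scores, so levels at each visit can be shown. What is missing is a named paired change with an interval.

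It would also be wrong to say that r measures only the direction of change. The signed-rank statistic ranks absolute changes, so their relative size enters. A statistic based on direction alone would be a sign test.

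Since r is undefined, other readings are possible. The matched-pairs rank-biserial form also has a ceiling, at 1. A t-based r has no such fixed ceiling but crowds towards 1: for a 47-point gain it is 0.970 at an assumed SD of 12.

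Finally, the Protocol describes the work as follows: "A non-randomized, exploratory study, with repeated measures for pain and disability, was conducted". Its aim is to find variables associated with a successful injection, and the within-group r feeds none of those analyses. This limits the weight of the point but does not remove it, because the SAP itself chose to report the size of change.

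**Conclusion.** The point holds as a minor one about reporting. As the SAP's named measure of the size of paired change, r is unit-free, undefined as to formula and denominator, and limited to 0.87 or 0.62 with 29 untied pairs. Its practical weakness is lost resolution among large gains: at an assumed SD of 15, mean r is 0.82, 0.87 and 0.87 for gains of 20, 30 and 47 points.

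This rests on two assumptions: that r is Z/√N, and that the changes are roughly normal with an SD in the range shown. The documents do not say whether gains in this trial fell in the flat range. Small and large gains remain distinguishable when directions are mixed. The Wilcoxon tests, the Pull Test comparisons and the responder analyses are unaffected.

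**What to change.** For baseline to one week, baseline to six weeks, and one to six weeks, name the paired change in SPADI points and in NPRS points, with a 95% CI, as the measure of magnitude. Use the Hodges-Lehmann estimate with the interval that belongs to the signed-rank test, so that estimate and test agree. Describe it as a pseudomedian that equals the median change only if the changes are symmetric. Entry at a SPADI of 20 or more, on a bounded scale, does not assure symmetry, so show the median change beside it.

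If r is kept, state its formula and whether N counts pairs or observations, and describe it as a standardised signed-rank statistic, not as the size of the change.

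The cost is a short addition to the SAP and six short calculations (three comparisons × two outcomes) on scores the study already collects. No test changes and no further data are needed.

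### The Pull Test group comparison on average NPRS and SPADI (total) does not adjust for baseline scores, so it cannot show what the Pull Test adds beyond baseline severity and may lose precision at N = 29

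*SAP*

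**What the plan says.** The SAP (Statistical Analysis) describes the group comparison in one sentence: "Mean differences (Mann-Whitney) in average NPRS and SPADI (total) score for positive and negative Pull Test groups were analyzed for follow-up periods". It then reports r² values that "were calculated to identify the percentages of variability in the dependent variables (SPADI, NPRS) explained by each Pull Test group". The only regression is called univariate; it "was used to determine if demographics, clinical variables and clinical tests were predictive of successful response one-week and six-week post-CSI".

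The Protocol (Testing Sequence) shows that baseline data exist: pre-injection NPRS and SPADI "were then completed to identify changes over the follow-up period". The inclusion criteria set only a lower limit for disability, "SPADI (total) score greater than or equal to 20", so baseline severity can vary among those enrolled. Study Design calls the trial "A non-randomized, exploratory study, with repeated measures for pain and disability", and the sample is small: "29 participants were included from a consecutive convenience sample of 38 patients".

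For this comparison, neither document states a significance level, an effect size, a standard deviation, the Pull Test split, the correlation of baseline with follow-up, or baseline scores by group.

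**The concern.** Pull Test status is observed, not assigned, so nothing in the design balances baseline severity between positive and negative patients. If positive patients tend to start worse or better, part of a follow-up difference, and part of the r² credited to the Pull Test, could reflect where patients started.

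Whether that matters depends on the question. If the question is only whether the groups differ at follow-up, a Mann-Whitney test on follow-up scores answers it. If a reader wants to know whether the Pull Test says more than the pre-injection score already says, neither the test nor the r² can answer.

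Separately, with 29 patients, leaving out a baseline measured on the same scale can cost precision.

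**Working it through.** **Step 1. Does any listed analysis combine the Pull Test with a baseline score?**

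| SAP analysis | Baseline score | Pull Test | Both together |
|---|---|---|---|
| Friedman / Wilcoxon | yes, by implication | no | no |
| Mann-Whitney and r² | only if changes were compared | yes | not as a covariate |
| Fisher's exact test | no (dichotomous variables) | yes, as a clinical test | no |
| Univariate regression | not stated | yes, as a clinical test | no, one predictor at a time |

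None does. If the Mann-Whitney test used changes, baseline enters by subtraction but is still not conditioned on.

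**Step 2. Precision.** The plan gives no power figure to reproduce. From the Protocol: N = 29. Assumed: 15/14 split, 0.8 SD effect, two-sided .05, equal baseline distributions, correlation rho = .3, .5, .7.

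Variance factor v, relative to follow-up scores:
- follow-up scores: 1
- changes: 2(1 − rho)
- baseline-adjusted: (1 − rho²) × 26/25, where 26/25 allows for the extra covariate

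Power ≈ Φ(0.8 / (√v × √(1/15 + 1/14)) − 1.96), with √(1/15 + 1/14) = 0.372. For follow-up scores, 0.8/0.372 = 2.153, and Φ(0.193) = .576. For adjustment at rho .5, v = .780 and √v = .883; 2.153/.883 = 2.438, and Φ(0.478) = .684.

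The simulated columns (20,000 runs per cell) use rank methods throughout, so the gain does not come from switching to a normal model.

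| rho | v: scores / changes / adjusted | Approximate power | Simulated: Mann-Whitney scores / Mann-Whitney changes / rank ANCOVA |
|---|---|---|---|
| .3 | 1 / 1.400 / .946 | .576 / .444 / .600 | .509 / .385 / .545 |
| .5 | 1 / 1.000 / .780 | .576 / .576 / .684 | .514 / .504 / .615 |
| .7 | 1 / .600 / .530 | .576 / .794 / .840 | .509 / .725 / .757 |

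The gain depends on what was compared. At rho .3 it is small over scores (.545 − .509 = .036) but larger over changes (.545 − .385 = .160). At rho .7 it is large over scores (.757 − .509 = .248) but small over changes (.757 − .725 = .032). At rho 0, adjustment costs almost nothing (.515 against .510). With an assumed 22/7 split, scores give .404/.398/.399 and rank ANCOVA .429/.486/.614.

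**Step 3. Error if the groups differ systematically at baseline.** Assume a gap of 0.5 SD and a 15/14 split.

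- If the Pull Test has no effect given baseline, the expected follow-up difference is rho × 0.5 = .15/.25/.35 SD, and the expected change difference has size (1 − rho) × 0.5 = .35/.25/.15 SD. Both unadjusted readings can reject too often.
- If both groups change equally, the change difference is 0, but the adjusted coefficient expects (1 − rho) × 0.5 = .35/.25/.15 SD. Here the adjusted test rejects too often for that null.

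| Null hypothesis | Scores | Changes | Rank ANCOVA |
|---|---|---|---|
| No effect given baseline | .062/.089/.132 | .109/.091/.072 | .050/.049/.052 |
| Equal change | a true follow-up difference | .046/.046/.047 | .153/.122/.092 |

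Repeat runs move the highest cells by up to about one point (to about 14% and 16%). With a 0.2 SD gap the highest error is 6% under the first null and 7% under the second. With no gap, Mann-Whitney on scores and rank ANCOVA both stay at about 4% to 5%.

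**Step 4. What a rank-based adjusted estimate means.** The difference in mean ranks equals N × (U/(n1 × n0) − 0.5). So 0.5 + b/N, with b the group coefficient from the rank regression, is on the same scale as the unadjusted U/(n1 × n0). It is not the probability for two patients with equal baselines. For normal data, 0.8 SD and rho .7, that probability is Φ(0.8/√(2 × .51)) = Φ(0.792) = .786. With balanced baselines the probability is Φ(0.8/√2) = Φ(0.566) = .714. In simulation 0.5 + b/N averaged .716, and its 95% interval covered .786 in only 87% of samples. At rho .3 the distinction is trivial (.715 against .723).

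**The case against.** The strongest reply is that the study is exploratory and aims to find variables associated with a successful injection. The SAP never claims that the Pull Test adds to baseline severity, and it also reports sensitivity, specificity and likelihood ratios, which are unadjusted by nature. Unadjusted association is a legitimate target. This stands, and it keeps the point minor.

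Second, every numerical input beyond N = 29 is assumed, and the gain can be slight: about 4 points at rho .3 if scores were compared, and about 3 points at rho .7 if changes were. This also stands.

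Third, adjustment is not neutral. If equal change is the null of interest and a gap exists, the adjusted test is the inflated one. Four further tests also add to an already long exploratory list.

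Two stronger readings are tempting. A reader might infer that the comparison ignores baseline altogether; the sentence may refer to changes, which use baseline without adjusting for it. A reader might also infer that the Pull Test result is confounded by severity; no baseline difference between the groups is documented, so that is a possibility only.

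What survives is narrower: under either reading of the sentence, the listed analyses leave the conditional question unanswered, and the r² should not be read as the Pull Test's own contribution.

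**Conclusion.** The point holds as a minor limit on precision and interpretation. It rests on the text alone that no listed analysis conditions the Pull Test comparison on baseline, and that the compared quantity is not specified.

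Its size rests on assumptions. With 0.8 SD, 15/14 and balanced baselines, rank adjustment gives about 55%/62%/76% power at rho .3/.5/.7, against 51% at each rho on follow-up scores, or 38%/50%/72% on changes. If a 0.5 SD baseline gap existed, the 'no effect given baseline' null would be rejected in about 6% to 14% of samples on scores and 11% down to 7% on changes as rho rises, against 5% with rank adjustment. Under 'equal change', changes hold at 5% and rank adjustment gives about 16% down to 9%.

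These figures do not show that the reported comparison is biased, or that the adjusted analysis is the single correct one.

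**What to change.** 1. Keep the Mann-Whitney test and state whether it compared follow-up scores or changes.
2. Report baseline average NPRS and SPADI (total) by Pull Test group. Steps 1 and 2 are the most useful part and need only wording and one small table.
3. Add one baseline-adjusted comparison per outcome at one week and at six weeks (2 × 2 = 4 models), labelled post hoc and as a sensitivity analysis, with that outcome's baseline as the only covariate. For example, regress the ranks of follow-up on the ranks of baseline and Pull Test group. Take the p-value and confidence interval from the same coefficient, and give the partial r² beside the reported r². If 0.5 + b/N is shown, describe it as the probability that a positive patient has the higher score had the groups had the same baseline distribution, not as a comparison of two patients with equal baselines.
4. If baseline differs by group, show the change comparison as well and say that it answers a different question.

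The data already exist. The costs are one degree of freedom per model, four more exploratory tests on 29 patients with no multiplicity control, a scale less familiar than points, and little gain if baseline correlates weakly with follow-up. Other confounding remains; for example, "Each participant was allowed to continue their current physical therapy regimen if applicable".
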